8. Current or planned participation in an investigational new drug (IND) trial from 30-days prior to randomization through Day 14 post treatment.
9. History of full COVID-19 vaccination
 - a. Full vaccination is defined as >2 weeks post final vaccination dose

V. Investigational Product

Randomization, Blinding and Treatment Codes

This is a randomized, single-blinded controlled study. Subjects will be randomized 1:1 to receive Lambda 180 mcg SC injections vs. saline placebo injections.

Description and Handling

Lambda Formulation

Lambda injection is a sterile, nonpyrogenic, ready to use solution (0.4 mg/mL) that is clear to opalescent, colorless to pale yellow, and is essentially free of particles. Lambda injection is provided in a 1-mL long Type I glass syringe with a 29-gauge, ½-inch, thin-walled needle. The syringes are prefilled with a solution of Lambda Injection, mannitol, L-histidine, polysorbate 80, hydrochloric acid, and water for injections; they are intended for a single use (180 mcg dose). The study drug will be donated by Eiger Biopharmaceuticals. Swab kits and RT-PCR testing will be supplied by a contract research organization, Viroclinics.

Lambda Packaging and Labeling

Storage of the study drug will be done in the Massachusetts General Hospital Clinical Trials Pharmacy (MGH CTP) (directed by [name], PharmD). Study drug will be packaged and labeled per the Massachusetts General Hospital Investigational Pharmacy standard procedure and will adhere to federal guidelines.

Lambda Storage and Handling

Prefilled syringes should be stored in a refrigerator at 2 - 8°C (36 - 46°F) and protected from long-term (>24 hours) exposure to light. Lambda Injections should not be frozen. Until administered to the subjects, syringes containing the study drug should be stored in a secure area, accessible only to authorized site personnel or vendor (in the case of home health visits). During transport to subject homes (via ambulance vehicle for home health visits only), drug should be stored in a cooler with an ice pack. To ensure the stability and proper identification, study drugs should not be stored in a container other than the container in which they were supplied.

Saline Placebo

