In this single blind study, saline placebo injections will be prepared by the MGH CTP. Under the direction of the lead pharmacist, pharmacy staff will prepare the placebo injections by drawing up approximately 0.45 ml of sterile saline into a 1 ml Monoject Tuberculin Safety Syringe with a 28 gauge, ½ inch, thin walled needle. Placebo injections will be labeled with standard MGH research prescription EPIC label as peginterferon lambda-1a or placebo however the display name and administration instructions will be unblinded for provider to be able to choose the correct treatment.

Lambda/Placebo Administration

Each dose of study drug will be dispensed by the MGH CTP in the form of pre-filled syringes. Appropriately delegated, trained and credentialed study staff or contracted study vendor (in the case of home health visits) will administer the stud drug by subcutaneous injection. The injection site should be documented and entered into the EDC. The injection site may be any of the following locations:

- Upper outer arm (right/left)
- Front outer upper thigh (right/left)
- Abdomen
- Upper hip (Right/Left)

For active Lambda treatment only: prior to administration, credentialed staff will expel the air bubble from the syringe and set the dose by aligning the front edge of the stopper with the correct dose indicator line (180 mcg).

Prior and Concomitant Medications

Concomitant medications taken within 30 days prior to screening, up to and including 30 days after the last dose of study drug, need to be recorded in the source documents and electronic case report form(s) (eCRFs).

In drug-drug interaction studies in healthy subjects, the activity of select CYP enzymes were evaluated and suggest that following a single 180µg dose, Lambda is a mild inhibitor of CYP1A2, CYP2C9, and CYP3A4 and a moderate inhibitor of CYP2C19 and CYP2D6. Because the effects of these sensitive CYP substrates are mild or moderate, dose adjustments for other concomitant CYP substrates may not be necessary, but should be used with caution.

Accountability for Lambda/Placebo

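### The trial is called single-blind, but Lambda and placebo are presented and prepared differently, and little in the plan keeps this from the subject who rates the symptoms

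*Combined protocol and SAP*

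**What the plan says.** Section V, Randomization, Blinding and Treatment Codes: "This is a randomized, single-blinded controlled study". The Saline Placebo subsection repeats the single-blind description. It adds that the display name and administration instructions are unblinded so that the provider can choose the right product.

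The two products are described as follows.

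- **Lambda** (Lambda Formulation): "Lambda injection is provided in a 1-mL long Type I glass syringe with a 29-gauge, ½-inch, thin-walled needle". The solution is one "that is clear to opalescent, colorless to pale yellow".
- **Placebo** (Saline Placebo): about 0.45 mL of sterile saline in a "1 ml Monoject Tuberculin Safety Syringe with a 28 gauge, ½ inch, thin walled needle".
- **Preparation** (Lambda/Placebo Administration): "For active Lambda treatment only: prior to administration, credentialed staff will expel the air bubble from the syringe and set the dose". The dose is set by lining up the stopper with the 180 mcg indicator. No matching step is given for placebo.
- **Labeling:** the placebo label names peginterferon lambda-1a or placebo. Lambda is labeled under a pharmacy standard procedure that the document does not reproduce.

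Doses are given at baseline (Day 0) and Day 7 by site staff or, for home visits, by the contracted vendor. Section II makes symptomatic improvement, measured by daily questionnaire, a secondary objective. Section VIII compares symptom change between arms with a linear mixed model and safety events with Fisher's exact test.

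**The concern.** Because the person injecting knows the arm, the single-blind claim rests on what the subject can see. The container, possibly the look of the fluid, and one preparation step all differ by arm. The text describes no cover, no out-of-view preparation and no check of the blind.

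The ten-item questionnaire in Appendix 5 is rated by the subject. Section VI has the baseline questionnaire completed before randomization, and dosing follows. Any effect of expectation would therefore fall on the post-baseline scores, and so on the change that is compared. Adverse events that depend on subject report share this exposure. How much of that is collected is less clear, because the visit lists in Section VI name serious and procedure-related events.

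A subject who infers the arm may also be more or less willing to take the Day 7 dose or return for swabs. Section VIII removes subjects lost to follow-up on the ground that loss is unrelated to outcome.

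**Working it through.** **1. Does volume reveal the arm?** No. Lambda is a "ready to use solution (0.4 mg/mL"), and the dose is 180 mcg = 0.18 mg. Volume = 0.18 / 0.4 = 0.45 mL, the same as the placebo volume. The plan evidently meant to mask the subject and succeeded on volume.

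**2. What differs or matches at the point of use?**

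| Feature | Lambda | Placebo | Matched? |
|---|---|---|---|
| Nominal size | 1 mL | 1 mL | yes |
| Volume | 0.45 mL | about 0.45 mL | yes |
| Needle | 29 gauge, half inch | 28 gauge, half inch | nearly |
| Container | glass, prefilled, dose line | tuberculin safety syringe | no |
| Fluid | clear to opalescent, colorless to pale yellow | saline | overlaps |
| Air-bubble and dose-line step | yes | none described | no |
| Label naming both possibilities | not stated | stated | unclear |

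The container and the preparation step differ in every case. The fluid may or may not differ.

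**3. How large could the effect on symptoms be?** The documents give no symptom SD, bias size or guess rate, so this is an illustration only. Assume no true effect, 10 per arm (Section VIII), two-sided alpha 0.05 (assumed) and a two-sample t-test at one time point as a stand-in for the mixed model. A reporting bias of b SD gives noncentrality b × √(10/2) = 2.236b on 18 degrees of freedom.

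| Assumed bias b (SD) | Noncentrality | False-positive rate |
|---|---|---|
| 0 | 0 | 5% |
| 0.2 | 0.447 | 7.1% |
| 0.3 | 0.671 | 9.7% |
| 0.5 | 1.118 | 18.5% |
| 0.8 | 1.789 | 39.5% |

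**4. Does it reach the primary endpoint?** Swabs go to a central laboratory, so knowledge of the arm does not alter the reading. The plan's 94% chance of at least 3 PCR-negative Lambda subjects reproduces: with a 50% rate, 1 − (1 + 10 + 45)/1024 = 0.945. It does not depend on blinding.

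The remaining route is loss to follow-up. At the plan's expected 5/10 in the Lambda arm (50%), losing one PCR-positive subject gives 5/9 = 55.6%, and losing one PCR-negative subject gives 4/9 = 44.4%. In the control arm the plan expects no PCR-negative subjects. There, 0/10 and 0/9 are both 0%, so drop-out would move the control estimate only if that expectation is wrong.

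**The case against.** The best case for the plan has four parts.

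- **Where the step is done.** A reader might infer that the Lambda-only step happens at the bedside. The document says only that it comes before administration, so it could be done at a medication station. This stands. The gap is that nothing requires it to be out of view, and both site and vendor staff give doses.
- **What one subject can deduce.** Each subject receives one product, so there is no side-by-side comparison, and the second dose shows the same presentation again. Size, volume and needle are close, and Lambda may look like saline. Nothing says that subjects are told what either syringe looks like. So it is not shown that subjects will identify their arm, only that they could. A factory glass syringe with a dose line, or tinted fluid, can still be informative alone.
- **Masking not written down.** A reader might conclude that no masking is used. The text does not support that. It describes a shared label for placebo and refers Lambda labeling to a pharmacy procedure outside the document. What can be said is that the visible text describes nothing further.
- **Limited consequence.** PCR is read centrally. The rule for further study in Section VIII rests on PCR negativity, with viral load also considered, and symptoms do not enter it. This stands and limits the weight of the point.

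One related route is separate. Appendix 5 lets study or clinical team members write down dictated answers, with no requirement that they be unaware of the arm.

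**Conclusion.** The point holds as a weakness in a stated design feature. Followed as written, the plan allows the one party meant to be blinded at the injection to infer the arm on either dosing day. The change is worth making, because the symptom comparison is a stated secondary efficacy objective and the remedy is nearly free.

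Two stronger readings are tempting. The first is that any guessing better than chance abolishes the single-blind property. Partial guessing weakens a blind by degrees, and the documents give no guess rate. The second is that the primary result is compromised. PCR is exposed only if drop-out differs by arm, and the documents give no basis for estimating that.

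The 7% to 40% range depends entirely on the assumed bias of 0.2 to 0.8 SD, the assumed alpha and the simplified test. It shows sensitivity at 10 per arm and is not a forecast.

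**What to change.** In Section V, Lambda/Placebo Administration, add three requirements for site and vendor staff alike.

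1. In both arms, complete all syringe preparation, including the existing Lambda dose-setting step, out of the subject's sight.
2. Before approaching the subject, place the same opaque cover over either syringe. For Lambda this comes after the dose is set. A sleeve fitted earlier by the pharmacy would hide the line that staff must align.
3. Use the same label, naming both possibilities, on both products. State this under Lambda Packaging and Labeling as well as Saline Placebo.

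Leave the Lambda-only dose-setting instruction as it is and add no sham dose-setting to placebo. No 180 mcg line is described on the placebo syringe, and out-of-sight preparation makes a sham step unnecessary. The drug stays in its supplied container, so the storage rule in Section V is not affected.

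The cost is a simple cover, a line in the site and vendor instructions, and about a minute more per injection. The needle and safety device may still be visible, so the masking would be improved but not complete. This change does not close the separate question of who records dictated questionnaire answers.

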- To assess the efficacy of Lambda (180 mcg SC injections) vs. saline placebo injection in inducing PCR negativity at days 3, 7 and 14 among hospitalized subjects with symptomatic COVID-19 infection
- To assess the efficacy of Lambda (180 mcg SC injections) vs. saline placebo injection in inducing symptomatic improvement in subjects with COVID-19 infection, assessed by daily symptom questionnaire
- To assess the efficacy of Lambda (180 mcg SC injections) vs. saline placebo injection in improving clinical outcomes (death, ICU stay, intubation) in subjects hospitalized with COVID-19 infection
- To evaluate the safety and tolerability of Lambda (180 mcg SC injections) vs. saline placebo injection

III. Study Design

This is a prospective randomized trial to assess the antiviral efficacy of Lambda (180 mcg SC injection) vs. standard of care in up to 20 subjects hospitalized with COVID-19 infection.

Visit schedule

After referral by the care team and informed consent, and once the subject is confirmed as COVID-19 positive on clinical testing, patients will have initial clinical lab testing performed during baseline (visit 1). After confirmation of inclusion criteria, patients will be randomized 1:1 to receive the first dose of Lambda or saline placebo at the baseline visit (visit 1). Nasal swabs for PCR analysis will be collected for all subjects on Days 3, 7 and 14. An optional Day 5 nasal swab collection will occur only for subject who remain hospitalized on Day 5. On day 7, subjects in the treatment arm will receive a second Lambda injection and subjects in the control arm will receive a second saline placebo injection. On Day 14, subjects will undergo laboratory measurements to confirm CBC and LFT values are within safe parameters. Research blood will be collected and stored for future testing to measure levels of pro-inflammatory cytokines (e.g. IFN- γ , IL-6, IP-10, MCP-1, TNF- α). Measurements will be performed using excess blood collected for clinical purposes wherever possible. Subjects will complete a daily symptom questionnaire from screening through Day 14 ([Appendix 5](#)).

Administration of Treatment

Upto an initial 30 hospitalized patients will be enrolled (consented), with a goal of 20 subjects randomized 1:1 to receive either Lambda 180 mcg SC injections or saline placebo injections.

Administration of first dose Lambda/placebo in relation to initial COVID-19 symptom onset will be documented in all subjects.

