- Complete physical examination including vital signs (resting blood pressure, pulse, respiratory rate and temperature), body weight, and height
- Collect 30ml research blood for storage and future immune biomarker testing
 - Immune biomarkers include IFN- γ , IL-6, IP-10, MCP-1, TNF- α
- Collect sputum and saliva for storage
- Review of clinical lab results for
 - Chemistry
 - Hematology
 - Coagulation
 - Pregnancy testing in WOCBP

Clinical labs drawn within 48 hours prior to consent will be used for screening and as baseline. If clinical labs required to determine protocol eligibility are not available, the clinical care team will be notified and if clinically indicated, testing should be ordered by the care team per standard practice. If testing is not clinically indicated, testing may be completed after informed consent is obtained as part of study screening.

- Request completion of baseline symptom questionnaire
 - Baseline symptom questionnaire must be completed prior to randomization.

From the time of obtaining informed consent through the first administration of study drug (Lambda or saline placebo), all serious adverse events (SAEs), as well as any adverse events related to protocol-mandated procedures, will be recorded in the source and on the adverse events case report form (CRF/eCRF). It is expected the first administration of study drug will occur within 24 hours of informed consent but will occur no later than 72 hours after most recent COVID test, as defined by time of clinical sample collection. All other untoward medical occurrences observed during the screening period, including exacerbation or changes in medical history are to be captured on the medical history CRF/eCRF.

See [Appendix 3](#): Adverse Events and Toxicity Management for additional details.

After review of inclusion and exclusion criteria to confirm continued eligibility, subjects will move into the baseline portion of the visit and be randomized to study drug or placebo assignment. Study drug or placebo will be administered on-site by appropriately credentialed and trailed staff. Up to 30 patients will be consented with a plan of 20 patients randomized to receive Lambda or placebo. A 10 patient cap will be placed on the Lambda treatment group, study enrollment will be halted if this cap is reached.

The following will be performed and documented:

- Review of inclusion/exclusion criteria
- Review of concomitant medications taken since previous visit

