This is a pilot study to assess the ability of Lambda to increase the proportion of subjects with PCR negativity at Day 7 compared to standard of care (placebo group) as a primary endpoint. We anticipate that no subjects in the standard of care arm will be PCR negative at Day 7, and we anticipate that 50% of subjects in the Lambda arm will be PCR negative at Day 7.

The treatment will be considered for further study if the proportion of subjects who achieve PCR negativity will be 30% higher at Day 7 in the Lambda arm compared to the standard of care arm. This would correspond to 3/10 subjects in the Lambda arm if 0/10 subjects were PCR negative in the standard of care (placebo) arm. Assuming 50% of subjects will be PCR negative, we have a 94% chance of observing 3 or more subjects who are PCR negative at Day 7. This shows that our sample size of 10 subjects per group is sufficient to have a reasonable chance to support further study given the proposed treatment effect. Additionally, demonstration of a reduction in viral load relative to the placebo arm will be factored into decisions to pursue further trials.

IX. References

3. Loutfy MR et al. Interferon alfacon-1 plus corticosteroids in severe acute respiratory syndrome: A preliminary study. *JAMA* 2003 Dec 24/31; 290:3222-8.

Appendices

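### Enrolment halts when the Lambda arm reaches 10, giving a 50% chance of fewer than the stated 10 controls; how many are lost depends on a randomisation method the protocol does not give

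*Combined protocol and SAP*

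**What the plan says.** Four places in the combined protocol and SAP bear on the number of controls.

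- Section VI, Pretreatment and Baseline Assessments (Baseline Visit): "Up to 30 patients will be consented with a plan of 20 patients randomized to receive Lambda or placebo". The next sentence adds: "A 10 patient cap will be placed on the Lambda treatment group, study enrollment will be halted if this cap is reached".
- Section III, Study Design, describes a trial in "standard of care in up to 20 subjects hospitalized with COVID-19 infection" and, under Administration of Treatment, "with a goal of 20 subjects randomized 1:1 to receive either Lambda 180 mcg SC injections or saline placebo injections".
- Section V, Randomization, Blinding and Treatment Codes, gives the 1:1 ratio. It names no block size, list length or stratification.
- Section VIII, Sample size and power calculation, sets the decision rule at a 30-point difference, illustrated as 3/10 against 0/10, and concludes that "our sample size of 10 subjects per group is sufficient to have a reasonable chance to support further study". Its control assumption is: "We anticipate that no subjects in the standard of care arm will be PCR negative at Day 7".

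**The concern.** The halt applies to the whole study but is triggered by one arm. When the tenth Lambda subject is randomised, any placebo place not yet filled is lost. No section sets a minimum for placebo, lets placebo recruitment continue, or requires a balanced list to be completed. The section VI rule therefore does not deliver the 10 controls that section VIII states.

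At stake are the primary Fisher comparison, the Day 7 viral-load t-test and the safety comparisons in section VIII. That section also removes subjects lost to follow-up, and the sample size makes no allowance for them, so there is no reserve of controls.

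**Working it through.** **Inputs.** From the protocol: 1:1 allocation (section V); at most 20 randomised and a halt at 10 on Lambda (sections III and VI); 50% PCR negative on Lambda, 0% on placebo and a 30-point rule (section VIII). Assumed, because not stated: two-sided 5% for the Fisher test; recruitment does not end early for another reason; nobody is randomised after the halt.

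**1. The plan's own figure.** With X ~ Binomial(10, 0.5), P(X ≥ 3) = 1 − (1 + 10 + 45)/1024 = 968/1024 = 0.945. This agrees with the stated 94%. It uses the 10 Lambda subjects only.

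**2. Chance of falling short.** Take the first 19 places of the allocation sequence. One arm must hold at least 10 of them and the other at most 9. If Lambda holds at least 10, enrolment has already halted with at most 9 controls; otherwise there are at least 10 controls. When the arms are treated symmetrically the two cases are equally likely, so P(fewer than 10 controls) = 0.500. Simulated permuted blocks of 2 to 20 gave 0.498 to 0.501.

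**3. How many controls are lost.**

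- *Blocks of 2.* After nine blocks the count is 9/9. If the last pair is Lambda then placebo (probability 1/2), the trial ends 10 against 9; otherwise 10 against 10.
- *Blocks of 4.* After four blocks the count is 8/8, and the last block has six equally likely orders. One (LLPP) ends 10 against 8: 17%. Two (LPLP, PLLP) end 10 against 9: 33%. Three end 10 against 10: 50%.
- *One balanced list of 20.* The mean number of placebo places after the last Lambda place is 10/11 = 0.91. Simulation puts 6 or fewer controls at about 4%.
- *Simple randomisation.* P(halt with k controls) = C(9+k, k) × 0.5^(10+k). The sum over k = 0 to 9 is 0.500, and k = 10 gives 0.088. The remaining 0.412 reach 20 with fewer than 10 on Lambda. Mean controls when short: 6.5. P(7 or fewer) = 0.31; P(6 or fewer) = 0.23.

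For comparison, simple randomisation of 20 with no halt gives P(fewer than 10 controls) = 0.412. Under that scheme the halt adds 0.500 − 0.412 = 0.088 to the frequency.

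**4. Effect on the plan's decision probability.** At 0% control negativity, 3/10 − 0/n is 30 points for any n, so 0.945 does not move.

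**5. Effect on Fisher power, 50% against 0%.** With no PCR-negative controls, significance needs this many PCR-negative Lambda subjects out of 10:

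| Controls | Needed | Power |
|---|---|---|
| 7 to 10 | 5 | 638/1024 = 0.62 |
| 5 to 6 | 6 | 386/1024 = 0.38 |
| 3 to 4 | 8 | 56/1024 = 0.05 |

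**6. Effect on precision.** With equal variances, the standard error of a difference in means scales with √(1/10 + 1/n): 0.447 for n = 10, 0.459 for n = 9, 0.474 for n = 8 and 0.516 for n = 6. These are increases of about 3%, 6% and 15%.

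**7. Effect on the 30-point rule when a control is PCR negative.** 4/10 − 1/10 = 30.0 points and passes; 4/10 − 1/9 = 28.9 points and does not. At an assumed control rate of 10%, which the protocol does not give, the chance of passing is 79.5%, 68.1%, 70.7%, 73.2%, 74.1% and 77.5% with 10, 9, 8, 7, 6 and 5 controls.

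**The case against.** The case for leaving the rule alone has four parts.

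*The harm is small under the plan's own assumptions.* This stands for modest losses. With blocks of 2 or 4, neither the 94% nor the Fisher power at 50% against 0% changes. It does not stand for simple randomisation, which the protocol does not rule out: 23% of trials would have 6 or fewer controls.

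*The halt is not the only cause.* A reader might infer that the halt alone produces the shortfall. Under simple randomisation that is wrong, since 41% of trials would fall short without it; there the halt mainly makes the shortfall deeper. Under a balanced list or blocks that divide 20, the halt is the whole cause.

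*The decision-rule example is selective.* A reader might take the fall from 79.5% to 68.1% as information lost with one control. It is not. The chance of passing rises again as more controls are lost, so the drop reflects the coarse steps of a 30-point threshold, at a control rate the protocol does not state. Section VIII also lets viral load reduction enter the decision. What stands is narrower: allocation order alone can change whether the threshold is met.

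*Sizes are ceilings or goals, and completing a 10 + 10 list has a cost.* The wording in sections III and VI is indeed that of a maximum or a target, but section VIII then treats 10 per group as the size that suffices. The cost is real. Once ten Lambda places are used, every remaining place is placebo, and section V leaves the treatment display unblinded to providers. The halt avoids this predictability, but small blocks limit it to the last one or two places.

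**Conclusion.** The point holds as an inconsistency between the enrolment rule and the stated group size. The 50% needs only symmetric 1:1 allocation and recruitment that runs to the halt or to 20. The size of the shortfall cannot be fixed from the protocol: it is one or two controls with blocks of 2 or 4, and can be several with simple randomisation.

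A reader might infer that the trial's power is halved, or that the 94% is wrong. The documents support neither. The 94% reproduces and does not involve the controls when their PCR-negative rate is 0%. Fisher power drops only at 6 or fewer controls, and those power figures rest on an assumed two-sided 5% level. For smaller losses the cost is some precision in the viral-load and safety comparisons, and sensitivity of the 30-point rule if any control is PCR negative. The point should be corrected because the remedy is cheap; it does not by itself undermine the design.

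**What to change.** Replace the halt sentence in section VI with wording such as:

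*Subjects are allocated from a concealed permuted-block list, held by the pharmacy, containing exactly 10 Lambda and 10 placebo places. No more than 10 subjects receive Lambda. Enrolment ends when all 20 places are filled.*

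This keeps the Lambda cap, supplies the missing randomisation method, and gives 10 per group once enrolment completes. It needs no extra Lambda and nobody beyond the 20 already planned.

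There are two costs. In about half of trials the last placebo subjects take slightly longer to recruit. The last one or two placebo places may also be predictable to unblinded staff, so the block size should be small and not disclosed to recruiting staff. Blocks of 4 limit the predictable run to two places. Blocks of 2 limit it to one, but let anyone who sees the assignments deduce the second place of every pair.

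If the sponsor prefers to keep the halt, section VIII should say that 10 controls are not assured, and section V should state the method so that the likely shortfall is known.
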